6.2. Study Population

6.2.1. Subject Disposition

Subject disposition will be presented by treatment group and overall, including the number screened, the number of screen failures and the number randomized. The study disposition will also be presented along with the reasons for early study withdrawal.

The number of subjects in each analysis set will be presented on the Randomized Population by treatment group and overall.

The following by-subject listings will be presented.

- Study completion information, including the reason for premature study withdrawal
- Visit dates
- Inclusion in study Analysis Sets and reason for exclusion from the IEP
- Protocol deviations

6.2.2. Demographic Characteristics

Demographic characteristics at enrollment (i.e., at the time of informed consent) will be presented. Summary will include the following: age, sex, ethnicity, race, height, weight, body mass index.

Medical history will be coded using Medical Dictionary for Regulatory Activities (MedDRA) and summarized alphabetically by System Organ Class (SOC) and Preferred Term (PT).

Table summaries to be produced by treatment group and overall and repeated for the Randomized Population, the Safety Population and the Immunogenicity Evaluable Population.

Demographic characteristics and medical history data will also be provided in data listings on the Randomized Population.

6.2.3. Prior and Concomitant Medication

Prior and concomitant medications will be coded using the WHO Drug dictionary.

Prior medications will be defined as any medications with a start date strictly before the date of study vaccine administration.

Concomitant medications will be defined as any medications with a start date on or after the date of study vaccine administration, as well as medications taken prior to the study vaccine administration and continuing after.

If a medication date or time is missing, or partially missing, and it cannot be determined whether it was taken on or after start of treatment, it will be considered a concomitant medication.

Results will be tabulated by Anatomic Therapeutic Class level 2 and preferred term.

Table summaries to be produced by treatment group and overall on the Safety Population.

Prior and concomitant medications will be included in a by-subject data listings.

6.2.4. Exposure and Compliance

Frequency and percentage of subjects with vaccinations will be summarized. For subjects who received a vaccine, the administered vaccine will be summarized.

Table summary to be produced by treatment group on the Randomized Population.

6.3. Efficacy Evaluation

Not Applicable.

6.4. Safety Evaluations

All Safety summaries to be produced by treatment group on the Safety Population.

6.4.1. Adverse Events

6.4.1.1. Solicited Adverse Events

Solicited AEs are protocol-specified local and systemic symptoms/events that are proactively collected from the subject and evaluated by the Investigator or designee. Solicited AEs are collected for 7 days after each injection, starting on Day 1, within an electronic diary.

Solicited AEs for this study are:

- Local events: Pain, Erythema (redness) at the injection site, Edema (swelling) at the injection site
- Systemic events: Fever (oral temperature $\geq 100.4^{\circ}\text{F}$), Fatigue, Headache, Muscle pain, Joint pain

The Subject and the Investigator will grade all AEs for severity from "mild" (grade 1) to "potentially life-threatening" (grade 4), except for severity of redness and swelling recorded as diameters (cm) and graded accordingly (see Guidance for Industry Toxicity Grading Scale for Healthy Adult and Adolescent Volunteers Enrolled in Preventive Vaccine Clinical Trials, September 2007 for details on grading scale).

Only Solicited AEs collected in the diary CRF, within 7 days after vaccine administration (i.e. from Day 1 to Day 7) will be analyzed in this Section. Occurrence of a solicited AE on a specific Day will be identified by a Grade ≥ 1 for that AE on that day.

Solicited AEs continuing beyond 7 days after injection will be combined with unsolicited AEs and described separately as specified in Section 6.4.1.3.

The following characteristics will be calculated:

- Maximum severity (Investigator):

For each solicited AE collected for a subject, the maximum severity will be the highest grade recorded, as per Investigator, for all occurrences of this AE within 7 days of vaccine administration (i.e., from Day 1 post-administration to Day 7) for the overall summary, or within a single day for the summary by day. There will be no replacement in case of missing severity.

- Maximum relationship (Investigator):

For each unsolicited AE collected for a subject, the maximum relationship will be the strongest relationship, as per Investigator, for all occurrences of this AE. There will be no replacement in case of missing relationship.

- Time of first onset of first event (days):

Day of onset of the first solicited AE, as per the nominal visit where the first solicited AE was first reported (as per Investigator). This will range from 1 (Day 1 = Day of study vaccine administration) to 7 (Day 7).

- Duration of solicited AEs (days):

Number of days between the onset of the solicited AE (i.e. nominal visit of first occurrence of Grade \geq 1) and the end of the solicited AE (i.e. nominal visit when Grade is back to 0).

If there are different occurrences of a same solicited AE within 7 days, the durations will be added up.

For solicited AEs continuing beyond 7 days, the end day of the continuing event will be used as end day for the calculation.

Example: If a subject has a Fatigue starting on Day 2 and finishing on Day 3. And a new Fatigue starting on Day 7 and ending on Day 9. The Duration will be 1+2=3.

If the solicited AE is ongoing (i.e. stop date is missing), then duration will be the Number of days between the onset of the solicited AE and the study discontinuation date.

Frequencies and percentages of subjects experiencing each solicited AE will be presented overall and by severity. For each of the time points or time intervals presented in the summaries, only subjects with at least one observation (i.e., any non-missing values but excluding "Not done/unknown") for the solicited AEs will be summarized.

The following summaries of subjects will be performed:

- Solicited AEs within 7 days post-injection, for each event and for any event, overall and by maximum severity. Details by category (local, systemic) will also be presented. (Severity as per Investigator)
- Solicited AEs by day post-injection, for each event and for any event, overall and by severity. (Severity as per Investigator)
- Solicited AEs by day post-injection, for each event and for any event, overall and by severity. (Severity as per Subject)

- Time of first onset of solicited AEs within 7 days post-injection for each event and any event. Duration of each solicited AEs and maximum duration for any event. (Severity as per Investigator)

Listings of all solicited AEs will be provided by subject.

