5.10 Solicited Adverse Events

Solicited AEs will be collected for 7 days, after the injection, starting on Day 1. Solicited AEs for this study are local events of pain, erythema (redness) and edema (swelling) at the injection site, and systemic events of oral temperature $\geq 100.4^{\circ}\text{F}$, fatigue, headache, muscle pain, and joint pain.

Subjects will receive and be trained on the use of a paper diary to observe, measure, and record these solicited AEs. The diary will serve as the primary source document and data will be entered by the site into the subject visit solicited AE form in the EDC system. A digital thermometer will be provided to the subject to measure oral temperature each day, and it is to be recorded daily in the diary. To record injection site local reaction, a ruler will be provided to the subject to measure the diameter of redness and swelling at the largest point of the reaction each day; it is to be recorded daily in the diary.

Subject is to be instructed to immediately call the study site if they experience a grade 3 (severe) or grade 4 (life threatening) symptom. Study site will determine if the subject needs to return to the site for safety evaluation and follow-up.

Study staff will review the signs and symptoms recorded in the diary and the action taken for the event during the subject's next scheduled clinic visit (Day 8). The Investigator will assess all recorded solicited events for severity and relatedness during this subject visit. Severity will be graded according to the FDA Toxicity Grading Scale (FDA 2007). The results of the Investigator's assessment, if different from the subject's entry, will be recorded in a separate field specified for Investigators within the EDC system.

Symptoms continuing beyond the solicited AE collection period (7 days following the injection) will be collected and recorded as an unsolicited AE in the source document.

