6.1.3 Day 8 (+3 days)

The following procedures will take place at this visit:

- Review of diary data with the subject; Investigator's assessment of severity and relationship to study vaccine
- Review of concomitant medications
- AE (solicited and unsolicited) and SAE evaluation

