6.1.4 Day 29 (\pm 3 days)

The following procedures will take place during this visit:

- Review of concomitant medications
- AE (unsolicited) and SAE evaluation
- Blood collection for serum sample for immunogenicity

6.1.5 Months 3 and 6 (90 to 180 days after Day 1 (\pm 5 days))

These visits are follow-up phone calls for safety evaluation. The following procedures will take place at each visit:

- SAE, NOCI, and MAAE evaluation
- Review of concomitant medications associated with SAEs, NOCIs, MAAEs, or prohibited medications

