6.2 Early Discontinuation Visit

All subjects who discontinue study participation before the Month 6 visit will be requested to undergo an Early Discontinuation visit.

If the visit occurs within 7 days after study vaccine administration, the following will be conducted:

- Review of diary data with the subject; Investigator's assessment of severity and relationship to study vaccine

- Review of unsolicited AEs and SAEs
- Review of concomitant medications associated with new or ongoing AEs and any SAEs
- Blood collection for serum sample for immunogenicity

If the visit occurs after Day 8 and before Day 29, the following will be conducted:

- Review AEs and SAEs
- Review concomitant medications associated with new or ongoing AEs and any SAEs
- Blood collection for serum sample for immunogenicity

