6.3 Unscheduled Visits

Any study procedure, excluding study vaccination, may be conducted at an unscheduled visit as needed. Examples may include repeat physical examination, vital signs, blood collections, and additional safety follow-up for an AE.

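### Does a blank Investigator grade leave the 7-day severity of solicited reactions undefined?

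*SAP*

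**What the plan says.** Protocol 5.10 makes the subject's diary the primary source for solicited events. At the Day 8 visit, "The Investigator will assess all recorded solicited events for severity and relatedness during this subject visit". On recording, it adds: "The results of the Investigator's assessment, if different from the subject's entry, will be recorded in a separate field specified for Investigators". The visit list in Protocol 6.1.3 matches: "Review of diary data with the subject; Investigator's assessment of severity and relationship to study vaccine".

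SAP 6.4.1.1 has both the subject and the Investigator grade events. For the 7-day summary, "the maximum severity will be the highest grade recorded, as per Investigator, for all occurrences of this AE"; a missing severity is not replaced. Onset is also taken from the Investigator's record. Occurrence on a given day is a grade of at least 1 in the diary CRF, without saying whose grade. The planned tables are:

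- 7-day maximum severity, by Investigator grade;
- severity by day, once by Investigator grade and once by Subject grade;
- onset and duration, by Investigator grade.

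All solicited events are also listed by subject.

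Two general rules apply. SAP 6.1.1 has categorical tables show how many subjects have missing data. SAP 6.1.6 rules out imputation, with one exception: a systemic solicited event without a relationship entry counts as possibly related.

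**The concern.** Taken together, the two documents seem to leave a hole. If the Investigator's field is filled only on disagreement, most fields will be blank. A table built on that field with no replacement would then have little to report. Even if a blank is read as agreement, an unreviewed diary leaves the same blank.

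An unreviewed diary is possible. Diary review is scheduled at Day 8 and at an early discontinuation visit within 7 days of vaccination. The Day 29 list has only "AE (unsolicited) and SAE evaluation". The early discontinuation list that opens "If the visit occurs after Day 8 and before Day 29, the following will be conducted" does not name the diary. Protocol 6.3 permits a catch-up ("Any study procedure, excluding study vaccination, may be conducted at an unscheduled visit as needed") but does not require one.

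The severity rows belong to the first two primary safety endpoints, and arms hold 50 subjects. Severe reactions may be few, so one subject handled differently could visibly change a row. Redness and swelling are graded from measured diameters, so the question is mainly about pain, headache, fatigue, muscle pain and joint pain.

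**Working it through.** The plan states no figure on this point, so there is none to reproduce. The check sets the passages side by side and then sizes the effect under stated assumptions.

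**What a blank means.**

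1. *Diary reviewed, field blank.* Protocol 5.10 requires every recorded event to be assessed and a separate entry only on disagreement. A blank is then the protocol's own record of agreement. The Investigator's grade equals the diary grade, and nothing is missing.
2. *Diary not reviewed, field blank.* The recording rule concerns the result of an assessment. With no assessment there is nothing to agree with, so the Investigator grade is missing. SAP 6.4.1.1 leaves it missing, in line with SAP 6.1.6, and SAP 6.1.1 puts it in the missing count.

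**Can the two be told apart?** Not from the severity field alone. SAP 6.2.1 lists visit dates by subject, which show who had no Day 8 visit. Relatedness must also be assessed for every solicited event (Protocol 5.10 and 7.3) and has no rule limiting entry to disagreements. A completed entry therefore points to a review. An absent one is weaker evidence, since SAP 6.1.6 allows for it.

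**Why the blank-means-no-event reading would not survive.** Assume 20 of 50 subjects react by diary (40%) and the Investigator changes the grade for 10% of them, still at grade 1 or more. Counting only filled fields gives 0.10 × 20 = 2 subjects, and 2/50 = 4%. With 5% or 20% changed it gives 2% or 8%. Such a table would clash openly with the Subject-grade table by day and with the listings.

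**Size for unreviewed diaries.** Inputs: n = 50 per arm (SAP 2.3). By assumption, 30 subjects react by diary (60%) and u of them are unreviewed. The severity rows sum to (30 − u)/50, with u in the missing count.

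| u | Severity rows | Missing severity | Any reaction by diary |
|---|---|---|---|
| 0 | 30/50 = 60% | 0 | 60% |
| 1 | 29/50 = 58% | 1 | 60% |
| 2 | 28/50 = 56% | 2 | 60% |
| 5 | 25/50 = 50% | 5 | 60% |

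SAP 6.4.1.1 keeps anyone with at least one observation in the denominator. If unreviewed subjects were dropped altogether, the percentage would lie between (30 − u)/(50 − u), when all of them reacted, and 30/(50 − u), when none did:

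- u = 1: 59.2% to 61.2%
- u = 5: 55.6% to 66.7%

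The Wilson 95% interval for 30/50 is 46.2% to 72.4%, so even five unreviewed diaries stay well inside the sampling error of one arm.

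**A sparse row.** Assume 2 of 50 (4%) have grade 3 by diary and one is unreviewed. The row then shows 1/50 = 2%, with one subject missing. For 2/50 the Wilson interval has centre (0.04 + 3.84/100)/(1 + 3.84/50) = 0.0728 and half-width 1.96 × √(0.04 × 0.96/50 + 3.84/10,000)/(1 + 3.84/50) = 0.0618. That is 1.1% to 13.5%, and it contains both values. Protocol 5.10 also tells subjects to telephone the site at once for grade 3 or 4 symptoms, which makes an unseen severe event less likely.

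**The case for a change.** The best case for a change is that neither document says how a blank is read. Protocol 5.10 records by exception, whereas SAP 6.4.1.1 speaks of both parties grading everything. Two programmers could handle the same blank differently. SAP 6.1.6 also foresees solicited events without one Investigator assessment, relatedness, and gives a rule for it, while severity gets only non-replacement. No 7-day maximum table by Subject grade is planned to fall back on, and a clarifying sentence would cost almost nothing.

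The mismatch in wording does stand. It has little consequence because the two readings apply to different situations: agreement after a review, missing without one. Whether the Investigator field is mandatory is a matter for the CRF, which is not among the documents. Nor are its completion guidelines, and SAP Section 5.5 is not visible in the public text. If the field is mandatory, the ambiguity vanishes.

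The route to an unreviewed diary is also narrower than it looks. Day 8 has a 3-day window. Protocol 7.2, 7.3 and 7.5.2 require severity and relationship for all events, with no Day 8 limit. The later early discontinuation list covers adverse events generally, not just unsolicited ones.

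Filling blanks from the diary for unreviewed subjects is not clearly better. It would put ungraded self-reports into a table labelled as the Investigator's, beside a separate Subject-grade table. Keeping the two sources apart is a fair choice.

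The diary description is inconsistent too. Protocol 5.10 says "Subjects will receive and be trained on the use of a paper diary", while SAP 6.4.1.1 and its schedule of events describe an electronic one. That is a clerical slip about data collection and alters no planned analysis.

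**Conclusion.** No change to the plan is needed. A blank after a review means agreement, and without a review it means a missing grade that the tables already count. Analysts with the visit dates and CRF in hand would reach this convention and could note it in the programming specifications.

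The possible effect is 2 percentage points per unreviewed reactor in an arm of 50, moved from a severity row to the missing count. Diary-based occurrence does not move, and no bias in the primary percentages is shown. Onset and duration could be affected for the same few subjects, but the documents give nothing with which to size that.

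This rests on three assumptions: occurrence is read from the diary CRF, the Day 8 review is carried out when the visit takes place, and missed reviews are few. The documents give no rate for the last, and the counts above are illustrations.

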9.5.3 Unsolicited AEs

All the unsolicited AEs occurring during the study will be recorded, regardless of their assessment of relatedness by the Investigator.

The original verbatim terms used by Investigators to identify AEs will be mapped to preferred terms using the MedDRA dictionary. The unsolicited AEs will then be grouped by MedDRA preferred terms into frequency tables according to system organ class (SOC). All reported AEs, as well as AEs judged by the Investigator as at least possibly related to study vaccine, will be summarized by treatment group, according to SOC and preferred term within SOC. When an unsolicited AE occurs more than once for a subject, the maximum severity reported and strongest reported relationship to the treatment group will be counted.

Only TEAEs will be summarized as defined in [Section 7.1.1](#). The selection of unsolicited AEs and their assignment to time intervals will be done by day of onset and not by days ongoing/persisting.

Unsolicited AEs will be summarized by alphabetic SOC, and preferred term as follows:

- Any unsolicited TEAE
- Possibly or probably related unsolicited TEAEs
- SAEs
- Possibly or probably related SAE
- Unsolicited TEAE leading to withdrawal
- Any AE leading to death

Listings of all TEAEs will be provided by subject.

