6.1.6. Missing, Unused, and Spurious Data

Binary endpoints / Continuous data:

Missing data are assumed to be missing at random and ignorable. Missing data will not be estimated or imputed. Denominators for percentages will be based only on the number of subjects with non-missing values. The only exception is:

- Systemic Solicited AEs with missing "Relationship to study vaccine" will be analyzed as "Possibly related".

Dates:

For partial or missing AE start dates the following imputation rules will be applied:

1. If year is not missing and is after the year of first dose:
 - a. If month is missing, then month will be imputed as January.
 - b. If day is missing, then day will be imputed as the first of the month.
2. If year is not missing and is the same as the year of the first dose:
 - a. If month is missing, then impute the month as the month of the first dose date.
 - b. If day is missing, and the month is the same as the month of the first dose date, then impute day as the day of the first dose date.
 - c. If day is missing but month is after the month of first dose date, then impute day as the first day of the month.
3. If year is missing, then impute the year as the year of the first dose date:
 - a. If month is missing, then impute the month as the month of the first dose date.
 - b. If day is missing, then impute the day as the day of the first dose date.
4. If the start date is completely missing, but the AE is either ongoing (i.e. AE stop date is missing) or the stop date is after the first dose date then impute the start date as the first dose date.
5. For any cases involving the rules above, if the AE end date is before the AE start date, then do not impute the AE start date and assume that the AE is treatment emergent/concomitant for the purpose of the analysis. Further, if the AE stop date occurs prior to the first dose date, do not impute the AE start date, and assume that the AE is not treatment emergent.

No imputations will be applied to AE stop dates or other dates. As indicated above, AEs with missing stop date are considered ongoing.

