6.4.1.2. Unsolicited Adverse Events

An unsolicited AE is an AE that is spontaneously reported by the subject or discovered by the Investigator. SAEs, NOCIs and MAAEs would be recorded as part of the collection of unsolicited AEs as specified in the visit procedures. Unsolicited AEs are collected separately from solicited AEs.

Solicited AEs continuing beyond 7 days will be flagged using rules given in Section 5.2 and described in separate summaries as explained in Section 6.4.1.3.

The definition of a treatment emergent AE (TEAE) is an event that occurs after vaccination and within the 28 days after vaccination (i.e., excluding those after a subject has given informed consent, but before vaccination):

- Onset (days) = Start date of AE – Date of Study Vaccine Administration + 1
- An AE is a TEAE if Onset \geq 1 and Onset \leq 28

Adverse events are summarized by subject, therefore, in any tabulation, a subject contributes only once to the count for a given adverse event (SOC or preferred term).

Unsolicited AEs will be coded using the Medical Dictionary for Regulatory Activities (MedDRA) and will be summarized by decreasing frequency of SOC and preferred term within SOC in the control group, as follows:

- Any unsolicited TEAEs
- Possibly or probably related unsolicited TEAEs
- Unsolicited TEAEs leading to study withdrawal
- Any AE leading to death
- Any SAE within 6 months after the vaccination by maximum relationship to study treatment. This summary will include serious solicited AEs.
- Any NOCI within 6 months after the vaccination by maximum relationship to study treatment.
- Any MAAEs within 6 months after the vaccination by maximum relationship to study treatment.

Following by-subject Listings will be provided:

- Pre-vaccination AEs (non-emergent)
- All unsolicited TEAEs
- All post-vaccination SAEs, NOCIs and MAAEs

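### Unsolicited AEs with a blank relationship rating drop out of the related-TEAE table, and no unsolicited summary is by severity

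*SAP*

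**What the plan says.** **Relationship.** SAP 6.4.1.1, headed Solicited Adverse Events, contains a rule for unsolicited events: "For each unsolicited AE collected for a subject, the maximum relationship will be the strongest relationship". It closes with "There will be no replacement in case of missing relationship".

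SAP 6.1.6 sets the general position, "Missing data will not be estimated or imputed", and "Denominators for percentages will be based only on the number of subjects with non-missing values". It allows one exception, which begins "Systemic Solicited AEs with missing" and assigns a blank relationship to the possibly related category. Unsolicited AEs and local solicited AEs are outside it.

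SAP 6.4.1.2 uses relationship in four unsolicited summaries. One is "Possibly or probably related unsolicited TEAEs". The other three split SAEs, NOCIs and MAAEs by maximum relationship, and the SAE summary also takes in serious solicited AEs.

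**Severity.** Protocol 7.2 has the Investigator grade every AE. Protocol 9.5.3 says that when an unsolicited AE recurs in a subject, "the maximum severity reported and strongest reported relationship to the treatment group will be counted". The SAP defines maximum severity in 6.4.1.1 for solicited AEs only. No summary in 6.4.1.2 (unsolicited) or 6.4.1.3 (combined) is by severity. SAP section 7 declares one change, on the Day 29 data freeze and unblinding.

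**The concern.** The two missing-relationship rules point in opposite directions, and the SAP gives no reason. The cautious rule covers systemic solicited AEs, whose own summaries in 6.4.1.1 are built on severity, day, onset and duration, not relationship. The rule that leaves a blank as a blank covers unsolicited AEs, where relationship decides who is counted. The effect on the related-TEAE table is anti-conservative: an unrated event can only lower the count. The rule is also in the wrong section, so a programmer could apply it to the wrong events.

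On severity, the SAP carries over the relationship half of the protocol's counting sentence and leaves out the severity half. The primary objective is safety and tolerability at three dose levels. As planned, the report would have no by-arm count of severe unsolicited events, and a reader would have to build one from listings.

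**Working it through.** The plan states no figure on this point, so the check is mainly a comparison of text. The arithmetic only sets the scale.

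**Step 1. What happens to a blank rating.** Take one subject and one unsolicited TEAE term, and apply SAP 6.4.1.1 (strongest rating, no replacement) and 6.1.6 (exception not applicable). The third column follows SAP 6.1.1, which has categorical tabulations show the number of subjects with missing data.

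| Ratings recorded | Related-TEAE table | SAE, NOCI, MAAE tables by relationship |
|---|---|---|
| Possibly or Probably Related, plus blank | counted | shown at the recorded rating |
| Not Related, plus blank | not counted | shown as Not Related |
| blank only | not counted | at most shown as missing |

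The loss is therefore limited to the last two rows. In the overall row of the related table, a subject is lost only if no other AE of that subject is rated related. In every case the event still counts under any unsolicited TEAE and appears in the listings.

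**Step 2. Is the wording a slip?** If the word unsolicited in the 6.4.1.1 rule was meant to be solicited, the rule contradicts the 6.1.6 exception for systemic solicited AEs. Unsolicited blanks would still not be replaced, under the general rule in 6.1.6. Either reading needs correction and gives the same result for unsolicited AEs.

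**Step 3. Scale.** SAP 2.3 plans 200 subjects in four equal arms: 200/4 = 50, matching its stated 50 per arm. One affected subject moves the rate by 1/50 = 2.0 percentage points. For illustration, let R be the number of subjects in an arm who count as related when blanks are taken as possibly related, with one of them blank. R is an assumption, since neither document gives an expected count. The last column applies the non-missing denominator rule of 6.1.6.

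| R | Blank counted as possibly related, R/50 | No replacement, (R−1)/50 | No replacement, (R−1)/49 |
|---|---|---|---|
| 1 | 2.0% | 0.0% | 0.0% |
| 3 | 6.0% | 4.0% | 4.1% |
| 5 | 10.0% | 8.0% | 8.2% |

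**Step 4. Severity, source by source.**
- Protocol 7.2: all AEs are graded, so the data exist.
- Protocol 9.5.3, counting sentence: maximum severity and strongest relationship are both to be counted.
- Protocol 9.5.3, table list: no by-severity table is named.
- SAP 6.4.1.1: maximum relationship is defined for unsolicited AEs, maximum severity for solicited AEs only.
- SAP 6.4.1.2 and 6.4.1.3: no summary by severity.
- SAP section 7: silent.

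A rule for counting maximum severity does nothing unless some tabulation uses severity. The SAP provides none for unsolicited AEs.

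**The case against.** The strongest reply is that blanks should hardly occur. Protocol 7.3 requires a causality rating for every AE, 7.5.2 lists relationship and severity among the items recorded for each AE, and 7.6 requires causality on the SAE form. Queries are resolved and data cleaned before lock. No primary endpoint is defined by relatedness or by grade. All of this stands and limits the urgency. It does not explain why the SAP has opposite rules for the two kinds of AE.

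On severity, the reply is that the protocol's sentence governs recurrent events and its own list names no by-severity table, so the SAP has removed no table that the protocol named. That also stands. What remains is a counting rule that the SAP neither implements nor declares as dropped. Solicited AEs are tabulated by severity in detail, so tolerability is not left without any severity data.

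Three stronger readings are tempting, and the documents do not support them:
- That the systemic solicited exception does nothing. It acts through serious solicited AEs, which SAP 6.4.1.2 puts in the SAE table by maximum relationship. The use is narrow, but it exists.
- That a blank is treated as Not Related throughout. Under SAP 6.1.1 a wholly blank rating would appear as missing in the SAE, NOCI and MAAE tables. Only the related-TEAE table omits it, and only the mixed case becomes Not Related.
- That the missing severity table weakens the stopping rules. Protocol 7.9 acts on individual events during the vaccination period and does not depend on end-of-study tables.

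**Conclusion.** The point holds as two modest defects. First, the SAP's missing-relationship rules are inconsistent, and the one for unsolicited AEs is both misplaced and anti-conservative. It can lower the related-TEAE count by 2 percentage points per affected subject in an arm of 50, and it turns a mixed blank and Not Related record into Not Related. This is an inconsistency within the SAP, because the protocol sets no rule for missing relationship. Second, unsolicited AEs are graded but not tabulated by severity, although protocol 9.5.3 expects maximum severity to be counted, and section 7 does not mention it.

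The 2-point figure assumes the planned 50 per arm, a denominator of 50, and a subject with no other related rating. How many such subjects there will be cannot be known from the documents, and it should be few. A reader might want the shift as a share of the related count, but that needs an expected number of related events that neither document supplies. No primary safety percentage changes. The changes are worth making because they cost little.

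**What to change.** 1. Move the maximum-relationship rule from SAP 6.4.1.1 to 6.4.1.2 and delete its last sentence, the one on replacement.
2. Extend the exception in SAP 6.1.6: unsolicited AEs, including SAEs, NOCIs and MAAEs, whose relationship is still missing after query are analysed as possibly related. Footnote the number so handled in each arm.
3. Add to SAP 6.4.1.2 one table of unsolicited TEAEs by SOC, PT and maximum severity by treatment group, with a row for any Grade 3 or higher event. If the sponsor decides against it, section 7 should say so.

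All three should be settled before the treatment codes are opened, so that the choice is not made with results in view. The cost is a few sentences and one table from data already collected. The downside is a related-AE count that may look slightly less favourable.
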